3.3. Participant Retention

Aim 1 requires only a single interaction with participants. The intervention period for Aim 2 and 3 will last 60 days with assessments at baseline, 2-months and 6-months post intervention initiation. Upon enrollment, we will obtain contact information (e.g., two cell phone numbers, directions to households, and contact information for up to three other individuals) to facilitate tracking. For the pilot study in Aim 3, participants will also be provided with phones allowing us the capability to reach them via SMS or calls as an alternative to their main phone number. Participants will be contacted regularly (e.g., twice a month) to update contact information and check on location. Prior to the assessment visits, reminder calls and SMS messages will be made to both partners one week before the appointment and again 1-2 days prior. For participants who miss appointments, we will limit the number of phone call attempts to 3-4 to respect privacy and the right to refuse. There may be special circumstances when outreach workers will be dispatched to participants’ homes (with their prior consent) such as when calls do not go through.

We anticipate that we will lose a very small percentage of couples due to break-ups, deaths, and migration (<5% in another study at the site called *Uthando Lwethu*), which we have accounted for in recruitment and analysis plans. One assessment will be conducted with each partner separately following the break-up to understand when the couple broke up, whether study participation contributed to the break-up, and if not, other reasons for why the couple broke-up. The breakup assessment will also allow us to identify any negative effects of participation on couples. If the study contributed to the break-up or the break up was a negative experience, we will follow the adverse event logging process. We will continue to follow each partner individually and administer study assessments given that our study outcomes (e.g., alcohol use) are at the individual level. This will allow us to explore whether participation in the intervention, despite the break-up, still had an effect on their alcohol use. However, couples who break-up before participation in the intervention will exit the study.

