4.0 Intervention Description

The two intervention arms consist of standalone MI (arm 2) and MI *Plus* (arm 3), which consists of MI sessions in arm 2 plus use of the mobile breathalyzer and app for two months. Both intervention arms are conducted with the couple as a unit.

MI *Plus* will consist of: 1) manualized MI sessions with couples and a counselor; 2) handheld breathalyzer with accompanying mobile app to deliver real-time feedback on drinkers' BAC levels to both partners. BAC data collected will be also used to provide personalized feedback based on summarized displays (e.g., calendar) of BAC levels in the MI sessions.

MI Sessions: We will aim for around 3 in-person sessions over a 60-day period with each session lasting 60-75 minutes – consistent with the format used in the Couples Health Project. We will administer MI sessions that are structured and manualized, as a roadmap for moving through content. MI is a collaborative process between a counselor and client, aimed at exploring and resolving ambivalence towards changing a behavior. Our approach will center around four MI processes (engagement, focusing, evoking, and planning)[30] and a fifth process around relationship quality based on co-I [name]' MI framework for couples[19, 20]. [name] recently published a paper using qualitative data from a couple-based MI intervention that supports the necessity of including relationship quality as a fifth MI process when working with couples.[31] An exploration of dyadic strengths is necessary to support couples with divergent views in the resolution of interpersonal ambivalence and the development of shared goal. [name] developed structured activities for exploring couples' shared goals and a lexicon of counselor skills that are effective in responding to dyadic ambivalence and achieving accommodation.[20]

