Outline of MI Sessions: The first session will occur within two weeks after baseline and the two subsequent sessions will be delivered at 30 and 60 days after couples have used the breathalyzer app. In the first session, the counselor will establish rapport and draw out the couples' communication strengths and weaknesses. The counselor will review baseline alcohol levels using this as a starting point to evoke change talk. The session ends with the creation of a goal to reduce alcohol use. Session 2 will review the BAC data (or self-reported alcohol use if in the non-breathalyzer arm) from the past 30 days using a calendar approach, a check-in on goals set in Session 1, and a review of communication successes and challenges. The session ends with the creation of a behavioral goal for the next session. Session 3 begins with a review of BAC data (or self-reported alcohol use if in the non-breathalyzer arm) from the past 30 days using a calendar approach, a check-in on goals set in Session 2, and ends with a discussion of long-term goals and related planning. If both partners are heavy drinkers, then couples will develop goals in each session for both partners.

Mobile Breathalyzer for Couples: We will use BACtrack View®, which consists of a handheld commercial-grade breathalyzer and mobile app. To avoid disruptions in cellular service by having to manually purchase data, we will automatically replenish participants' data when running low. To reach those who could greatly benefit from the intervention and to avoid

Couple-Based Motivational Interviewing with Mobile Breathalyzers to Reduce Alcohol Use in South Africa

widening the digital divide, we will provide phones to participants who do not have compatible smartphones.

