5.7 Recruitment and retention. We will recruit and randomize around 120 couples to meet our target sample size of 90 couples, assuming that we will lose around 25-30% of couples after randomization. We anticipate that we will lose a very small percentage of couples due to break-ups, deaths, and migration (<5% in Uthando Lwethu), which we have accounted for in recruitment and analysis plans.

5.8 Randomization process. After informed consent and the baseline assessment, couples will be randomized to either the control arm, the couple-based MI arm, or the couple-based MI with

Couple-Based Motivational Interviewing with Mobile Breathalyzers to Reduce Alcohol Use in South Africa

mobile breathalyzers arm (MI *Plus*). We will use randomly permuted block sizes (e.g., 3, 6, and 9) generated using a computerized and secure process. The UCSF project coordinator and the HSRC data manager will use the table that the statistician created to print documents that assign participants to one of the three arms. These documents will be placed in sealed envelopes and maintained by the HSRC data manager. HSRC interviewers will take a small subset of envelopes into the field with them. At the end of the baseline survey, the index patient will be given the envelope that contains the random assignment. Couples will receive an appointment card with a date for their next study visit following randomization.

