5.9 Control condition. Participants will receive the Usual Care (UC) defined by the South African national 2019 ART Clinical Guidelines (updated in March 2020). The harms of alcohol use are briefly discussed during the morning health talks in the waiting rooms of HIV clinics. HIV clients are advised that alcohol intake should be reduced to <2 standard drinkers/day for men and <1 for women for 5 out of 7 days per week. After randomization, couples in the control arm will receive brief alcohol counseling modeled off WHO guidelines and [name] intervention in Malawi, which uses participants' baseline AUDIT scores for messaging around alcohol reduction and lasts 5-10 minutes. In selecting the control, we chose to balance our ethical obligation to provide basic health information on alcohol use (minimal in this setting), while maximizing the generalizability of our findings to inform a future RCT, which will employ a UC control group. Clinical trial experts recommend the UC condition over other designs such as a time-and-attention control (TAC) when the long-term goal is to inform implementation science and scale-up. Our long-term goal will be to test the effectiveness of a scalable alcohol intervention. Moreover, because TAC designs have an active but different intervention, there is the risk of positively-biased intervention results because the comparison arm can distract participants from making reductions in alcohol use they would have otherwise made.

5.10 Procedures for mobile breathalyzers with couples in MI *Plus* arm. Drinkers will be provided with handheld breathalyzers and both partners will receive access to the breathalyzer results. Drinkers will receive SMS requests to take a breathalyzer test twice per day (e.g., in the morning at 11 am and in the evening at 8 pm). After the drinker completes each breathalyzer test, the partner receives a notification that the drinker completed a test and can view the test results. Partners will receive a unique login username and password linked to their study ID. [name] and the research manager(s) will facilitate a 1-2 hour training for couples how to use the breathalyzers/phones (e.g., charging, Wi-Fi, Bluetooth), complete breathalyzer tests, app functionality, trouble-shooting issues, and technical support. Couples will be instructed to use the breathalyzers for a 60-day period. Assessments at 60 days will allow us to assess the effects on alcohol use immediately following the 60-day intervention period.

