Engagement with mobile breathalyzer technology	Proportion of breathalyzer tests taken after prompted; number of partner SMS messages sent and received on BAC results; number of drinker SMS reminders to take breathalyzer tests sent and received; average length of time to take breathalyzer tests after prompted; average number of app logins per week to access BAC data (for both partners); average user session length; number of lost/stolen phones and breathalyzers	70% completion rate	3
Retention	Retention rates; reasons for dropouts	85% retention at 2-month follow-up	All
Process outcomes	Length of MI sessions in minutes	≤90 minutes per session[9]	2, 3
Intervention fidelity	Expert ratings of quality of intervention using audio-recorded intervention sessions (checklists)	>80% inter-rater reliability	2, 3
Assessment procedures	Length of surveys; proportion of couples who complete baseline, 1, 2, and 6-month surveys	90 minutes; 75% of all couples will complete all assessments	All

Couple-Based Motivational Interviewing with Mobile Breathalyzers to Reduce Alcohol Use in South Africa

Acceptability	Proportion of couples satisfied with the intervention. Couples will decide their satisfaction together since this is a dyadic intervention.	75% of couples reporting being satisfied or very satisfied	All
---------------	---	--	-----

Couple-Based Motivational Interviewing with Mobile Breathalyzers to Reduce Alcohol Use in South Africa

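### Couples who separate after randomisation but before participating in the intervention leave the study: a post-randomisation exclusion that may fall unequally on the arms, with feasibility denominators left undefined

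*Combined protocol and SAP*

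**What the plan says.** Section 3.3 treats break-ups in two ways. For couples who separate during the study the plan is: "We will continue to follow each partner individually and administer study assessments given that our study outcomes (e.g., alcohol use) are at the individual level". The paragraph then ends with an exception: "However, couples who break-up before participation in the intervention will exit the study".

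The timing comes from other sections:

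- **Randomisation (5.8):** "After informed consent and the baseline assessment, couples will be randomized to either the control arm, the couple-based MI arm, or" the MI-plus-breathalyzer arm. Allocation is disclosed at the same visit: "At the end of the baseline survey, the index patient will be given the envelope that contains the random assignment".
- **MI arms (4.0, outline of MI sessions):** "The first session will occur within two weeks after baseline".
- **Control (5.9):** "After randomization, couples in the control arm will receive brief alcohol counseling modeled off WHO guidelines". No interval is given.
- **Meaning of intervention (4.0):** the term is used for arms 2 and 3: "Both intervention arms are conducted with the couple as a unit".

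Table 4 in section 7.2 sets "85% retention at 2-month follow-up" for all arms, without a denominator. For arms 2 and 3 it also requires every couple to attend at least two of the three MI sessions. Section 3.3 says that the analysis plans allow for losses from break-ups, but section 7 defines no analysis population and no handling of couples who exit.

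**The concern.** The rule removes people who have been randomised and know their allocation, because of something that happens afterwards. This is the kind of exclusion that can undo the balance randomisation provides. Couples who separate early may well differ in drinking, conflict and adherence from those who stay together, and the chance of meeting the exit condition depends on how long each arm waits for its first contact.

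Three things are at stake:

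- **Arm comparisons (7.3).** H1, MI alone against control, is the most exposed. H2 is less so, because arms 2 and 3 share the same timing for session 1.
- **Feasibility verdicts (7.2).** Comparison with the Table 4 thresholds is the primary analysis, and a miss calls for changes before a full trial. Whether an exited couple stays in a denominator can matter there.
- **Follow-up information.** Leaving the study ends the later visits, at which partner violence would have been assessed, for people who parted just after allocation was disclosed.

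The rule also conflicts with the reasoning of its own paragraph. Outcomes are no less individual-level for a couple that parts on day 5 than for one that parts on day 50.

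**Working it through.** **1. The plan's own figure.** Sections 3.2 and 5.7 aim to keep 90 couples after 25-30% loss following randomisation, and 5.7 randomises about 120.

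- At 25% loss: 90 / (1 - 0.25) = 120, which reproduces the figure.
- At 30% loss: 90 / (1 - 0.30) = 128.6, so 129. Equivalently, 120 x 0.70 = 84 remain.

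The figure of 120 therefore matches the lower end of the stated loss. Section 2.5 instead describes 90 couples randomised, so both bases are used below. With equal allocation the two MI arms hold 60 couples (of 90) or 80 (of 120).

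**2. How many couples could be affected.** Section 3.3 expects under 5% loss from break-ups, deaths and migration together. As a ceiling for the MI arms:

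- 0.05 x 60 = 3 couples
- 0.05 x 80 = 4 couples

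The period for that 5% is not given. Assume losses spread evenly over T weeks, with T from 8.6 (two months) to 52 (one year). The expected number in a two-week window is then n x 0.05 x 2 / T:

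| MI couples | T = 8.6 weeks | T = 26 weeks | T = 52 weeks |
|---|---|---|---|
| 60 | 0.70 | 0.23 | 0.12 |
| 80 | 0.93 | 0.31 | 0.15 |

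So 0-1 couples is likely and 3-4 is the ceiling. Both include deaths and migration, which the rule does not concern.

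**3. Effect on the retention criterion if exits leave the denominator.** Take the largest number retained that still misses 85%, and remove b exits.

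| Randomised | b = 0 | b = 1 | b = 2 | b = 4 |
|---|---|---|---|---|
| 120 | 101/120 = 84.2% | 101/119 = 84.9% | 101/118 = 85.6% | 101/116 = 87.1% |
| 90 | 76/90 = 84.4% | 76/89 = 85.4% | 76/88 = 86.4% | not applicable (ceiling is 3) |

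Near the threshold, one exit (of 90) or two (of 120) change the verdict. Away from it they do not. At the planned loss, 90/120 = 75.0%, and removing the ceiling of 4 gives 90/116 = 77.6%. Reaching 85% would need a denominator of at most 90 / 0.85 = 105.9, so 15 couples would have to be removed.

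**4. Effect on the participation criterion.** A couple that parts before session 1 and leaves the study attends no session. Counted, one such couple gives 79/80 = 98.8% or 59/60 = 98.3%, and the 100% criterion is missed. Left out, it has no effect. This does not depend on being near a margin.

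**5. Exposure by arm.** In arms 2 and 3 the window runs from the baseline visit to session 1, up to 14 days. In control there are three possible readings:

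- Counselling counts as participation and is given soon after randomisation: the window is short and the rule falls mainly on the MI arms.
- Control care is not an intervention and the rule does not apply to it: it falls only on the MI arms.
- Control care is not an intervention and the rule is read literally: a control couple never participates, so a break-up at any time leads to exit, and the rule falls more on control.

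The text does not settle which is meant.

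**The case against.** The strongest case on the other side is that little follows from the rule. Probably no more than one couple is affected, the primary analysis is descriptive, and sections 7.3 and 7.4 label the arm comparisons exploratory and disclaim reliable effect sizes. The 101/120 example is the highest count that still fails, chosen at the edge. All of this stands, and it limits the weight of the point.

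A reader might infer more from the rule than the documents support:

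- **That it inflates retention.** Table 4 does not say that exited couples leave the denominator. Sections 3.3 and 5.7 speak of break-ups as losses. If they are counted as not retained, the rule lowers retention.
- **That it removes couples from the MI arms only.** This is the natural reading but not a stated one. Section 5.9 gives no interval for control counselling, section 5.8 speaks only of an appointment card for the next visit, and a literal reading reverses the direction.
- **That harm from an early break-up goes unrecorded.** Section 3.3 provides a separate assessment of each partner after a break-up, asking whether the study contributed, with a link to adverse event logging. Nothing limits it to later break-ups. Only the subsequent visits are lost.

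It can also be objected that keeping early separations in the participation denominator makes the 100% criterion fail after one such event. That is true. It shows how strict the criterion is, and is better faced openly than avoided by removing the couple.

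What the objection does not remove is that section 3.3 states a rule excluding randomised couples, against the reason given in the same paragraph.

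**Conclusion.** The point holds in a limited form. The exit rule is a post-randomisation exclusion, inconsistent with the plan's own reason for following later break-ups, and exposure to it probably differs by arm in a direction the text leaves open. The likely number is 0-1 MI couples and the ceiling about 3-4, assuming that the under-5% figure carries over to this trial and, for the likely number, that losses are evenly spread over 2 to 12 months. Bias in H1 and H2 is therefore likely modest.

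The retention verdict would change only if exits are dropped from the denominator and the result lies just under 85%; at the planned 75% it would not. The participation criterion is the more sensitive one, since a single couple decides it. The change is worth making because it is cheap and removes the ambiguity, not because a large bias is expected.

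**What to change.** Replace the exit sentence in section 3.3 with: *All randomised individuals, including those whose couple separates before the first session, are followed at 2 and 6 months in their assigned arm.* Whether and how sessions are delivered to separated couples is for the investigators and need not be part of this change.

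In section 7.2:

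- Define retention, participation and survey completion over all randomised couples (for participation, all those randomised to arms 2 and 3), and reconcile the 90 and 120 given as the number randomised.
- State what counts as participation in the control arm, and report pre-intervention break-ups by arm.

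The cost is a few sentences and a few extra individual assessments using procedures already in place for later break-ups. Feasibility figures may be slightly lower than if early exits were dropped from the denominators. One early separation in an MI arm would cause the 100% participation criterion to be missed, and the team should accept that knowingly before data are seen.

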3.4. Participant Withdrawal

Couples or individuals are free to leave the study at any time. If a participant notifies a staff member of their desire to withdraw from the study the staff member will ask if the couple or individual would like to share the reason they are withdrawing from the study. If the couple shares this information, the staff member will include that in their file and store their file in the “withdrawn participants” section of the filing cabinet. The project coordinator or project director must be notified of the situation.

4.0 Intervention Description

The two intervention arms consist of standalone MI (arm 2) and MI *Plus* (arm 3), which consists of MI sessions in arm 2 plus use of the mobile breathalyzer and app for two months. Both intervention arms are conducted with the couple as a unit.

MI *Plus* will consist of: 1) manualized MI sessions with couples and a counselor; 2) handheld breathalyzer with accompanying mobile app to deliver real-time feedback on drinkers' BAC levels to both partners. BAC data collected will be also used to provide personalized feedback based on summarized displays (e.g., calendar) of BAC levels in the MI sessions.

MI Sessions: We will aim for around 3 in-person sessions over a 60-day period with each session lasting 60-75 minutes – consistent with the format used in the Couples Health Project. We will administer MI sessions that are structured and manualized, as a roadmap for moving through content. MI is a collaborative process between a counselor and client, aimed at exploring and resolving ambivalence towards changing a behavior. Our approach will center around four MI processes (engagement, focusing, evoking, and planning)[30] and a fifth process around relationship quality based on co-I [name]' MI framework for couples[19, 20]. [name] recently published a paper using qualitative data from a couple-based MI intervention that supports the necessity of including relationship quality as a fifth MI process when working with couples.[31] An exploration of dyadic strengths is necessary to support couples with divergent views in the resolution of interpersonal ambivalence and the development of shared goal. [name] developed structured activities for exploring couples' shared goals and a lexicon of counselor skills that are effective in responding to dyadic ambivalence and achieving accommodation.[20]

Outline of MI Sessions: The first session will occur within two weeks after baseline and the two subsequent sessions will be delivered at 30 and 60 days after couples have used the breathalyzer app. In the first session, the counselor will establish rapport and draw out the couples' communication strengths and weaknesses. The counselor will review baseline alcohol levels using this as a starting point to evoke change talk. The session ends with the creation of a goal to reduce alcohol use. Session 2 will review the BAC data (or self-reported alcohol use if in the non-breathalyzer arm) from the past 30 days using a calendar approach, a check-in on goals set in Session 1, and a review of communication successes and challenges. The session ends with the creation of a behavioral goal for the next session. Session 3 begins with a review of BAC data (or self-reported alcohol use if in the non-breathalyzer arm) from the past 30 days using a calendar approach, a check-in on goals set in Session 2, and ends with a discussion of long-term goals and related planning. If both partners are heavy drinkers, then couples will develop goals in each session for both partners.

Mobile Breathalyzer for Couples: We will use BACtrack View®, which consists of a handheld commercial-grade breathalyzer and mobile app. To avoid disruptions in cellular service by having to manually purchase data, we will automatically replenish participants' data when running low. To reach those who could greatly benefit from the intervention and to avoid

Couple-Based Motivational Interviewing with Mobile Breathalyzers to Reduce Alcohol Use in South Africa

widening the digital divide, we will provide phones to participants who do not have compatible smartphones.

